### **Study end definition:**

- The study will end when the last participant has been completed and data has been collected. The study will close early if it is found during stage 1 that ultrasound is not useful (limited successful viewings of the vocal folds) in the assessment of vocal fold function.
- The trial will be discontinued if the feedback from patients is adverse for the experience of LUS, or in the case of any adverse events.

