The COVID-19 pandemic has restricted access and provision of standard SLT procedures including laryngoscopy, due to the risk of increased aerosol generation and disease transmission (Tran et al. 2012, Bolton et al. 2020, RCSLT 2020). Timely access to invasive diagnostic procedures, such as laryngoscopy has therefore been reduced from both staffing capacity and due to infection control and risk of transmission in COVID-19 positive patients.

Ultrasound is a potential addition to SLT instrumental tools as it is a non-invasive, non-ionising and non-aerosol-generating procedure that could be delivered at the bedside in a timely manner to assess laryngeal function. The use of ultrasound to identify patients who may have vocal cord movement impairments, such as vocal fold palsy and paresis has been shown to have high sensitivity and specificity in a recent systematic review and meta-analysis (Allen, Clunie & Slinger, et al 2020).

*The importance of recognising if a patient has ILO:*

The true prevalence of ILO is thought to be underestimated, with the European Respiratory Society and European Laryngological Society reporting that between 24% and 53% of patients with severe asthma have ILO. The prevalence of ILO in all asthma is estimated as 10% of the population.

Currently, there are approximately 5.4 million people in the UK receiving treatment for asthma. Therefore, potentially over half a million people in the UK may have ILO, the majority of whom may be undiagnosed.

Severe asthma affects 5 to 10% of the asthma population but consumes a disproportionate amount of the global asthma budget (~50%) due to unscheduled health care utilisation in primary care, hospitalisations due to severe exacerbations, and the costs of pharmacotherapy, some of which may not be necessary.

A recent systematic review (Lee et al 2020) highlighted ILO as a comorbidity in quarter to a half of asthma cases. In two prospective studies of difficult-to-treat asthma where ILO was suspected, up to 50% of patients were identified as suffering both ILO and asthma. (Low et al 2011, Forrest et al 2012).

A study from the Asthma UK Centre in Applied Research has found that asthma costs the UK health service at least £1.1 billion each year. A UK-wide study, by the Asthma UK Centre for Applied Research, found that there were around 6.4 million GP and nurse consultations for asthma each year. Around 100,000 people are admitted to hospital each year because of asthma attacks.

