### **Primary aims:**

To perform analysis of the range of vocal fold movements on inspiration, using TLUS in healthy volunteers and patients referred to a tertiary airways service.

To assess the sensitivity, specificity and positive predictive value of the use of ultrasound in the assessment of ILO, using Laryngoscopy as reference standard.

To investigate the patient and healthy volunteer perspectives of TLUS assessment of the vocal cords.

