## **Proposed methods:**

### **Stage one: healthy controls:**

Volunteers will be recruited from NHS staff at the host organisation (LTHTR). Healthy volunteers will be given an information leaflet and consent form upon providing an expression of interest.

Informed consent will be taken by the PI from healthy volunteers who decide to go ahead. It will be stressed that participation and consent can be withdrawn at any time. The consent process itself will take place before the procedure and will be taken by the PI (CS). Consent will be taken in a separate and private room (either the booking-in room in the endoscopy department at RPH, or a separate clinic room in the chest Clinic). This will be completed before the procedure and before entry into the room where the ultrasound procedure will take place.

The consent forms will be stored in a locked cabinet in PI's office. Longer-term, study documents including data and investigator site files will be archived at the Trust's off site archiving facility following local procedures.

Healthy volunteers will be allocated a time and date to attend Chest clinic, or the Endoscopy department at the host organisation, Royal Preston Hospital (RPH) for the scanning session. The scan will be carried out in a private room using transmission gel. Access only to the neck area is required, with privacy and dignity always respected.

The PI will perform an US scan of the larynx, using the Vscan Air (GE), using a protocol designed by the PI. The scan is recorded and stored securely using GE's system. A proportion of scan will be sent to the study collaborator ([name]) and a Specialist Head & Neck Sonographer securely and anonymously with no patient identifiable information included in order to confirm findings when there is uncertainty, and in order to ensure inter-rater reliability.

The scan will consist of a "sweep" of the larynx to identify the main landmarks (hyoid bone, thyroid cartilage, arytenoid cartilages, vocal cords and false vocal cords). A recording form has been prepared for ease of recording. An anonymised code number will be assigned to the Healthy volunteer.

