### **Stage two: patient population**

A sample of 30 participants will be recruited from consecutive patients referred to our NHS Tertiary Airways service for assessment for complex breathlessness and ILO. Participants will be asked at initial assessment, after they have consented to the laryngoscopy, if they would wish to undergo TLUS concurrently with their usual care of diagnostic laryngoscopy.

An information leaflet will be given, and written consent form completed with the patient by the PI. Written Information will be provided at the point of initial consultation (at least 48 hours before the planned procedure. Written consent will take place at the appointment for the Laryngoscopy (usual care for laryngoscopy), by the PI (CS). A witness will not be present. Consent will take place in a private booking-in room that is part of usual care for patients attending for laryngoscopy assessment for ILO). Patients have more than 48 hours to consider the information and decide if they would like to participate.

Patients who require an interpreter for their initial consultation will be provided with information via the interpreter of the study.

Patients will be informed that usual care will not be affected by their decision to participate or not, and that consent can be withdrawn at any point. If the patient finds dual assessment with laryngoscopy and TLUS too invasive or distressing, they can withdraw consent, and the TLUS will be stopped.

It is envisaged that the TLUS operator (PI) will perform the US assessment whilst another SLT completes the laryngoscopy (usual care) and works through the usual diagnostic laryngoscopy provocation protocol to induce symptoms. The US-operating SLT will take a note of settings to achieve image acquisition and will take note of vocal fold movements on an anonymised recording form with subject allocation number identified.

The SLT operators (TLUS and laryngoscopy) will be blinded to the images and results of the other assessment (either TLUS or laryngoscopy), as the screen for the Laryngoscopy system can be rotated away to be unobservable by the US-operator SLT. Following the procedure, the SLT conducting the US will leave the endoscopy theatre room to allow for usual debrief to occur with the patient (usual care). After this, the patient will be asked to complete a short questionnaire electronically to elicit their experience of TLUS.

<https://forms.office.com/pages/designpagev2.aspx?lang=en->

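### The stopping rule ends the whole trial for any adverse event, with no limit by seriousness or relatedness and no review step; a minor point, cheaply fixed

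*Combined protocol and SAP*

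**What the plan says.** The second bullet under Study end definition has two triggers. The first is: "The trial will be discontinued if the feedback from patients is adverse for the experience of LUS". The second follows directly: "or in the case of any adverse events". Both act on the trial as a whole, and the verb leaves no discretion.

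Other sections bear on how the second trigger would work:

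- **Interventions** says that laryngeal ultrasound has no known risks. It discusses procedural risk for ultrasound only.
- **Stage two: patient population** has TLUS done while a second therapist performs the laryngoscopy and "works through the usual diagnostic laryngoscopy provocation protocol to induce symptoms". The same section covers the individual patient who finds the "dual assessment with laryngoscopy and TLUS too invasive or distressing, they can withdraw consent, and the TLUS will be stopped".
- **Sample size** is given as "A sample of 30 participants will be recruited from consecutive patients" in the stage two section, and as up to 30 in Aims & Objectives. The number of stage one volunteers is not stated.
- **Monitoring, Reporting and Finance** commits in general terms to approvals, advice from relevant groups, the governance framework and GCP. **Data collection and handling** refers to a local procedure for research with healthy volunteers.

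**The concern.** An adverse event, without further qualification, includes trivial ones. A rule that must end the trial for any of them leaves the investigator two choices when something minor happens: stop the study, or depart from the written protocol with no stated basis. A hypothetical example is brief skin irritation after a scan, since "The scan will be carried out in a private room using transmission gel".

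It is also unclear which events count. The sentence opens with the experience of ultrasound, so TLUS events are the more natural scope. It does not exclude events from the concurrent laryngoscopy, however, and that procedure is usual care and is meant to provoke symptoms.

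What is at stake is mainly the second primary aim: "To assess the sensitivity, specificity and positive predictive value of the use of ultrasound in the assessment of ILO". That aim depends on stage two patients. The movement and participant-perspective aims also draw on stage one, so an early stop in stage two would affect them less.

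**Working it through.** **Step 1: is the rule qualified anywhere?** The sections were set against four possible limits.

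| Section | Seriousness | Relatedness | Number of events | Review before stopping |
|---|---|---|---|---|
| Study end definition | none | none | none | none |
| Interventions | none | none | none | none |
| Stage two (individual withdrawal) | none | none | none | none |
| Data collection and handling | none | none | none | none in the text; the local procedure is not reproduced |
| Monitoring, Reporting and Finance | none | none | none | general advice only, not tied to this rule |

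The plural form of the trigger sets no minimum count. The individual withdrawal provision acts on one patient's scan, so it does not limit a rule that acts on the trial.

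**Step 2: how likely is the rule to be triggered?** The plan states no stopping probability, so there is no figure to reproduce. The number of patients, n = 30, comes from the protocol. The event rate p per patient does not; it is assumed here at 0.1% and 1%, with patients treated as independent.

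Chance of at least one event in n patients = 1 − (1 − p)^n.

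| n | p = 0.1% | p = 1% |
|---|---|---|
| 10 | 1 − 0.999^10 = 1.0% | 1 − 0.99^10 = 9.6% |
| 20 | 1 − 0.999^20 = 2.0% | 1 − 0.99^20 = 18.2% |
| 30 | 1 − 0.999^30 = 3.0% | 1 − 0.99^30 = 26.0% |

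Stage one scans would add to this if their events count. With 10 to 30 volunteers (assumed), there are 40 to 60 scans in all, and the chance is 3.9% to 5.8% at 0.1% and 33.1% to 45.3% at 1%.

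**Step 3: what is the average loss?** If the trial stops at the first event, the expected number of stage two patients scanned, including the one with the event, is (1 − (1 − p)^30)/p.

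- At 0.1%: 0.0296/0.001 = 29.6 of 30.
- At 1%: 0.2603/0.01 = 26.0 of 30.

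**Step 4: what would a stop do to precision?** This assumes an observed sensitivity of 80% and inducible laryngeal obstruction (ILO) in half of the patients. For context, the Background cites that "between 24% and 53% of patients with severe asthma have ILO", which would be 0.24 × 30 = 7.2 to 0.53 × 30 = 15.9 patients, so one half is near the top of that range. Exact (Clopper-Pearson) 95% intervals:

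- 30 patients, 15 with ILO, 12/15 detected: 51.9% to 95.7%, width 43.8 points.
- 20 patients, 10 with ILO, 8/10 detected: 44.4% to 97.5%, width 53.1 points.
- 10 patients, 5 with ILO, 4/5 detected: 28.4% to 99.5%, width 71.1 points.

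The interval is already wide with all 30 patients. The two shorter cases are illustrations of a stop at exactly those points; step 2 shows how likely a stop by then is under each assumed rate.

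**The case against.** The strongest reply is that a strict stop is a legitimate cautious choice. This is a small pilot that includes healthy volunteers. No ultrasound risk is expected, so any TLUS event would be a surprise, and stopping errs towards the participants. What would be lost is pilot data; nobody would be harmed and no estimate would be biased. The sample is also described as up to 30, with no stated precision target, so falling short breaks no promised precision. Most of this stands, and it is why the point is minor. It does not answer the wording: a pause with review gives similar protection without committing the team to end the trial over something trivial.

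A second reply is that the probabilities have no anchor in the documents. This is correct. Taking the assumed rate from 0.1% up to 10% moves the chance of stopping within 30 patients from 3% to 96%. Such a range describes the assumption and says little about the plan.

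Three stronger readings are tempting and are not supported:

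- **That the trial is likely to stop early.** The documents give no event rate and expect no known risk from the scan.
- **That TLUS events could not be told apart from laryngoscopy events.** The stage two section mentions dual assessment as a possible source of distress, but its remedy is to stop the TLUS only. That keeps the research procedure separate from usual care, and the section says nothing about attributing events.
- **That no one would review an event in practice.** The general commitment to advice and GCP, and the local healthy-volunteer procedure, make some oversight plausible. They do not alter the rule as written.

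**Conclusion.** The point holds as a minor one. The protocol states a trial-level stopping rule that is broader than it needs to be: followed literally, one minor event ends the study. This rests on the text alone and needs no assumption about rates.

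The size of the harm is conditional and cannot be estimated from the documents. It is small if only TLUS events count and these are rare (29.6 of 30 patients scanned on average at an assumed 0.1%). It would be larger if laryngoscopy events also counted, but the text does not settle that they do. A reader might go on to infer that the plan contradicts itself or that the accuracy aim is compromised. Neither follows: the rule conflicts with no other statement in the protocol, and the accuracy estimate would be imprecise even with all 30 patients. The investigators may have meant only serious or related events, but the protocol does not say so.

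**What to change.** Under Study end definition, replace the adverse event clause with:

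> *Recruitment will be paused for sponsor review after any serious adverse event or any adverse event possibly related to TLUS or the combined procedure; the trial will be discontinued if the review finds a related serious event or judges that continuing is unsafe. Expected effects of usual-care laryngoscopy and intentionally provoked symptoms do not by themselves trigger discontinuation.*

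Leave the individual withdrawal provision in the stage two section as it is.

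The cost is two sentences of wording and a protocol amendment with ethics and R&D approval. No extra patients or procedures are needed. The safety stop becomes slightly less automatic, which the pause and review largely offset. Someone must also judge seriousness and relatedness when an event occurs, and the amendment should say which role does so. The separate trigger for adverse patient feedback is not changed by this wording.

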### **Monitoring, Reporting and Finance**

- The study will be conducted in accordance with approvals and advice from relevant groups e.g., Ethics and R&D Trust approval.
- The study will be conducted in compliance with the Research Governance Framework for Health and Social Care, the Medicine for Human Use (clinical trials) Regulation 2004 and Good Clinical Practice.
- No Financial agreements have been arranged.

### **Reporting and Dissemination**

Feedback will be given to patients via a poster in the waiting room, along with a scientific poster if successful accepted abstract.

Adapted from Southampton University Hospital Trust and United Bristol Healthcare NHS Trust Research and Development information sheets -  
Guide to writing a protocol for a non-Investigational Medicinal Product (IMP) randomised trial.
